[figure not shown]

**SECTION 1: Protocol Schema**

SECTION 2: BODY OF PROTOCOL

## 1 Introduction

### 1.1 Overview

The goal of this project is to develop and evaluate a multimodal sexual dysfunction intervention for survivors of allogeneic hematopoietic stem cell transplantation (HCT). The National Comprehensive Cancer Network (NCCN) identifies sexual dysfunction as a major issue facing cancer survivors that negatively impacts their quality of life (QOL) and mood. Allogeneic HCT survivors, like many cancer survivors, experience a significant and drastic deterioration in their sexual function that persists for many years following their therapy. In fact, sexual dysfunction is the most common and persistent long-term complication of HCT, adversely affecting patients' QOL, mood, and intimacy. Nearly half of HCT survivors are dissatisfied with the quality of their sexual life. Moreover, studies have clearly demonstrated that sexual dysfunction is associated with worse QOL, fatigue, emotional well-being, relationship satisfaction, and psychological distress. Thus, many allogeneic HCT survivors endure a significant deterioration in their sexual function, which adversely impacts their QOL and mood, and increases the overall morbidity of their treatment.

The etiology of sexual dysfunction post-transplant is multifactorial and includes problems with sexual desire and pleasure, hormonal deficiencies, vaginal and penile alterations secondary to graft-versus-host-disease (GVHD), delayed or absent orgasm and/or ejaculation, pain with intercourse, erectile dysfunction, and psychological problems such as anxiety, depression, and changes in body-image. Thus, an intervention that assesses a wide range of physical and psychological conditions is needed to address the range of sexual problems seen in this population.

Unfortunately, interventions to improve sexual function in HCT survivors are lacking. Additionally, clinicians are reluctant to address sexual function with their patients due to their lack of training and discomfort in engaging in these conversations. Given the well-documented burden of sexual dysfunction that allogeneic HCT survivors face, there is a compelling need to develop interventions that encourage clinicians to discuss sexual health issues with their patients, using a comprehensive and multimodal approach to address their diverse sexual needs.

In this project, we will develop and evaluate the efficacy of a multimodal sexual dysfunction intervention for allogeneic HCT survivors. The proposed project will proceed in two phases. During phase 1, we will conduct a prospective pilot study assessing the feasibility and preliminary efficacy of the intervention in improving patients' sexual function, QOL, and mood. During phase 2, we will conduct qualitative interviews with patients who completed the intervention to explore their perceptions of its acceptability, content, and efficacy, and the optimal timing for its delivery during their survivorship course. Data from this work will help inform a large-scale randomized study of a sexual dysfunction intervention for allogeneic HCT survivors.

The proposed project will assess an innovative and sexual dysfunction intervention that has the potential to substantially enhance the care of survivors of hematologic malignancies. Moreover, such an intervention can be adapted for use with other cancer survivors struggling with sexual dysfunction after their treatment. By implementing a multimodal intervention to improve sexual function, we aim to enhance the QOL, mood, and intimacy of cancer survivors.

### 1.2 Background and Significance

**The NCCN identifies sexual dysfunction as a major issue affecting many cancer survivors.** For allogeneic HCT survivors, sexual dysfunction is the most common and persistent long-term complication affecting patients' QOL, mood, and intimacy. Nearly half of HCT survivors are dissatisfied with the quality of their

## Sexual Dysfunction Intervention Post-Bone Marrow Transplant Protocol version 7/02-28-2017

sexual life. Studies have clearly documented worse psychosexual functioning in HCT survivors compared to healthy subjects and to those treated with chemotherapy alone. Notably, 45% of men reported a significant decline in quality and quantity of sexual function at 6 months, 1, 2, and 3 years after HCT compared to prior to transplant. Moreover, 40% of women are not sexually active at any time point post-HCT. **Thus, many allogeneic HCT survivors endure a significant and rapid deterioration in sexual function, which persists for many years after their treatment.**

Sexual health plays a central role in one's identity, QOL, and self-esteem; thus it is not surprising that sexual dysfunction causes increased distress and negatively impacts the QOL of cancer survivors. Research has shown that sexual function is associated with QOL, fatigue, relationship satisfaction, emotional well-being, anxiety, and depression. **Therefore, improving patient's sexual function post-transplant may have significant effects on their QOL and psychological distress, and decrease the overall morbidity of allogeneic HCT.**

**Allogeneic HCT survivors experience diverse problems affecting their sexual function.** Sexual complications include decreased libido, decreased pleasure, vaginal alterations, erectile and ejaculatory dysfunction, delay or absence of orgasm/ejaculation, premature menopause, sex hormonal deficiencies, dyspareunia, and infertility. Moreover, GVHD can affect the genital tract leading to vaginal stenosis and scarring. It can also cause scarring, adhesions and long-term injury to blood vessels with resulting arterial insufficiency, which manifests as erectile dysfunction in men and potentially anorgasmia in women. Finally, transplant itself can result in dermatologic changes and increased skin sensitivity affecting the genital tract. Lastly, problems with body-image, self-confidence, fear of disease recurrence, anxiety, depression, and concerns about infertility all play a major psychological role in affecting sexual function in transplant survivors. **Sexual dysfunction post-transplant is multi-factorial and requires a multimodal approach to care.**

**Despite its prevalence, health care providers are reluctant to address sexual dysfunction with cancer survivors.** In addition to insufficient time during an outpatient clinic visit, clinicians also cite lack of training and discomfort as barriers to discussing sexual dysfunction with their patients. Interestingly, patients who participated in a discussion with their health care provider about sexuality reported fewer sexual functioning problems at 3 years post-transplant compared to those who did not have any discussions. **Interventions are critically needed to improve the rate and content of conversations between clinicians and patients about sexual functioning post-HCT.**

**In addition to encouraging clinicians to discuss sexual health issues with their patients, we must develop interventions to improve patients' sexual function. Despite the tremendous well-documented burden of sexual dysfunction on allogeneic HCT survivors, interventions to improve sexual function are lacking.** Importantly, given the diversity of problems affecting sexuality in allogeneic HCT survivors, interventions must include a comprehensive assessment and a multimodal approach to address the diverse needs of this population. **While effective strategies exist to treat both female and male sexual dysfunction, interventions are critically needed to integrate these strategies into the care of allogeneic HCT survivors with an emphasis on their specialized needs.**

**In this project, we aim to develop and evaluate a multimodal sexual dysfunction intervention for allogeneic HCT survivors.** We will assess the feasibility and preliminary efficacy of the intervention in improving sexual function, QOL, and mood in transplant survivors. We will also use qualitative methods to explore patient's perception of the acceptability, content, and efficacy of the intervention and their preferences

for the timing of its delivery in the survivorship course. **Data from this work will help inform a large-scale randomized study of a sexual dysfunction intervention for allogeneic HCT survivors.**

### **1.3 Preliminary Studies**

#### *Quality of Life and Mood of Patients and Family Caregivers During Hospitalization for HCT*

We conducted a prospective longitudinal study of patients undergoing HCT to assess the impact of transplant hospitalization on patients' QOL and mood. We enrolled 97% of potentially eligible patients undergoing HCT. We administered patient reported measures to assess QOL and mood both weekly during their transplant hospitalization and at a follow up outpatient clinic visits, with a missing data rate of only 20%. Of note, we did not have any missing data from the outpatient clinic visits. This work demonstrates our research team's success in conducting longitudinal studies on patients undergoing HCT. Additionally, the findings from this work were used to develop a palliative care intervention specifically addressing the needs of patients undergoing HCT, which is currently being tested in a randomized clinical trial. Therefore, our team has prior experience developing innovative interventions targeting the needs of a particular population.

#### *Randomized Study of a Targeted Palliative Care Intervention in Patients Hospitalized for HCT*

We are currently conducting a randomized trial to evaluate the impact of a palliative care intervention on patients' QOL, mood, and symptom burden during hospitalization for HCT. The study opened for enrollment in August 2014 and to date we have enrolled 57 of 60 (95%) eligible participants. Only one participant (2.5%) withdrew and did not complete all patient reported measures. This work highlights our research team's experience conducting supportive care interventions in patients undergoing HCT. Moreover, it demonstrates our ability to successfully recruit and enroll transplant patients in intervention studies.

## **2 Objectives**

### *Quantitative Objectives and Hypotheses:*

- 1. To evaluate the feasibility of implementing a multi-modality sexual dysfunction intervention for allogeneic HCT survivors.**

*Hypothesis: We will be able to recruit 75% of patients who screen positive for sexual dysfunction causing distress to participate in a sexual dysfunction intervention, and 80% of participants will attend at least one additional follow-up or referral visit.*

- 2. To determine the preliminary efficacy of the intervention in improving sexual function, QOL, and mood.**

*Hypothesis: Participants will have improved sexual function, QOL, and mood at 6 months post-intervention compared to baseline.*

### *Qualitative Objective:*

- 1. To explore patients' perception of the acceptability, content, and efficacy of the intervention, as well as the optimal timing for intervention delivery during the survivorship course.**

### **3 Research Subject Selection**

#### **3.1 Study Subject Selection:**

We will recruit 53 allogeneic HCT survivors who are at least 3 months post-HCT and without evidence of disease from Massachusetts General Hospital bone marrow transplant clinic to participate in this prospective pilot study.

#### **Patients Eligibility criteria:**

1. Adult patients ( $\geq 18$  years) with hematologic malignancy who underwent an allogeneic HCT at least 3 months prior to study enrollment.
2. Ability to speak English or able to complete questionnaires with assistance required from an interpreter or family member.
3. Positive screen for sexual dysfunction that is causing distress based on the NCCN survivorship guidelines.

#### **Patient Exclusion criteria:**

1. Patients with relapsed disease post-HCT.
2. Significant psychiatric or other co-morbid disease, which the treating clinician believes prohibits the patient's ability to participate in the informed consent procedures.

### **4 Research Subject Entry**

#### **4.1 Study Research Subject Entry**

A total of 53 patients with hematologic malignancies who are 3 months after allogeneic HCT will participate in this study. All MGH transplant oncologists and nurse practitioners have agreed to participate in the study.

The research team will screen the weekly transplant clinic schedule to identify potentially eligible patients. The research staff will then inform the transplant clinician that the patient is eligible and inquire about any concerns regarding his or her study participation. If the transplant clinician has any objections regarding the patients' participation, we will document the reasons and not approach those individuals. If there are no concerns regarding study participation, the research team will attach a notification form to the patient's check-in sheet upon arrival to the transplant clinic. The form will instruct the transplant clinician to screen the patient for sexual dysfunction using the two-question approach based on the updated 2015 NCCN survivorship guidelines: 1) do you have problems with sexual function?; and 2) Are these problems causing you distress? The transplant clinician will then offer study participation for those individuals who screen positive for sexual dysfunction causing distress. If patients are interested in study participation, a member of the research team will then review the consent form with potential participants, which will clearly detail the nature of the study procedures, the time requirements, and frequency of the self-report questionnaires. The research team member will obtain written informed consent from participants and provide them with a copy of the signed consent form.

Study participants will complete baseline self-report assessments at the time of obtaining informed consent for the study or within the 72 hour window from study enrollment. Patients who provide informed consent and complete baseline questionnaires will then be registered with QACT and scheduled for their first study intervention visit on the same day as their regularly scheduled subsequent follow-up visit.

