## **5.2 Study Procedures:**

We will recruit 53 patients with hematologic malignancies 3 months after allogeneic HCT who report having sexual dysfunction causing distress for this study. Once written informed consent is obtained, patients will receive an outpatient multimodal sexual dysfunction intervention. The interventionist will rescreen the patients at the beginning of their initial visit. If patients no longer experience sexual dysfunction before their initial study visit, they will be considered ineligible for the study as they are no longer experiencing distress relating to sexual dysfunction. Because these patients have already signed consent, they will count towards accrual, but will no longer be eligible to participate in the intervention.

Prior to patients' enrollment on this study, we will train a total of two transplant clinicians regarding how to assess and address sexual dysfunction in the transplant clinic. [name] is the Director of the MGH Cancer Center Sexual Health Clinic and a world-renowned expert on sexual dysfunction in cancer survivors. He will first provide transplant clinicians with reading materials regarding how to assess and address sexual dysfunction. The transplant clinicians will review this literature prior to their didactic training sessions with [name]. [name] will then conduct two training sessions with the same two transplant clinicians prior to study enrollment to ensure they acquire the necessary skills to implement the sexual dysfunction intervention in the transplant clinic. One transplant MD and one experienced transplant nurse practitioner (NP) will be responsible for implementing the intervention in the transplant clinic.

[name] will first conduct a two-hour didactic training session with the transplant clinicians, focusing on the following areas:

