### 5.3 *Selection of study instruments*

#### • **Demographics:**

Patients will complete a demographic questionnaire at baseline detailing their age, sex, race, ethnicity, religion, relationship status (FC will specify their relationship with patients), educational level, annual household income, and living situation [appendix A].

- **Participant-reported measures:** We will administer the following questionnaires at baseline and 6 months after enrollment:
- **Male sexual function:** We will utilize the PROMIS Sexual Function and Satisfaction measures for men including the following domains: Global satisfaction with sex life, interest in sexual activity, erectile function, and orgasm [Appendix B].
- **Female sexual function:** We will utilize the Female Sexual Function Index (FSFI), which identifies problems with sexual desire and interest, sexual arousal, lubrication, reaching orgasm, pain with intercourse, and emotional closeness during sexual activity [Appendix C].
- **Patient-QOL:** We will use the Functional assessment of Cancer Therapy-Bone Marrow Transplant (FACT-BMT) to assess QOL, which has been validated for use in patients undergoing HCT [Appendix D].
- **Mood:** We will use the Hospital Anxiety and Depression Scale (HADS) to assess symptoms of psychological distress (depression and anxiety) [Appendix E], and the PHQ-9 to assess major depressive syndrome [Appendix F].
- **Qualitative Data Collection:** We will also conduct qualitative interviews with approximately 8 male and 8 female patients from the phase I participant pool to participate in the second phase. Participants must complete the 6-month post intervention assessment in phase I prior to enrolling in phase II. We will use a semi-structured interview guide to 1) explore patients' perception of the acceptability and content of the sexual dysfunction intervention; 2) explore patients' perception of the efficacy; and 3) identify the optimal timing of intervention delivery during the survivorship course. We will audi-record the interviews, transcribe them by Audio Transcription Center in Boston, MA, and code and analyze them using NVivo 10 software.

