### 5.4 *Administration and timing of self-reported measures:*

We will collect and enter all patient-reported data electronically using Research Electronic Data Capture (REDCap). The REDCap Survey is a tool for building and managing online surveys. Vanderbilt University, in collaboration with a consortium of institutional partners, has developed this software and workflow methodology for electronic collection and management of research and clinical trial data. Our research team has extensive experience using REDCap and will create and design the surveys in a web browser, with institutional information technology support. The REDCap Survey system offers secure, HIPAA compliant, web-based

Sexual Dysfunction Intervention Post-Bone Marrow Transplant  
Protocol version 7/02-28-2017

applications that provide an intuitive interface for participants to enter data, with real-time validation rules at the time of entry.

Participants will use tablet computers to complete questionnaires in clinic. If any participants refuse or are unable to complete the questionnaires on the computer, they will be permitted to use hard-copy paper versions. Participants who do not have a regularly scheduled clinic visit will be provided with remote access to REDCap system or paper-based questionnaire for home administration. The research team will contact patients twice to remind them to complete and return the surveys. If study participants fail to complete the surveys within the expected time point, we will report the data as missing and document the reason for incompleteness. Table 1 details the schedule for administering the self-report measures. All participants will complete baseline evaluation within 72 hours of study enrollment. All participants will then have a second evaluation at 6 months (+/- 2 weeks).

| Table 1              | Baseline (within 72 hours of informed consent) | 6 months from enrollment (+/- 2 weeks) |
|-----------------------------|---|---|
| Participant Measures |   |   |
| Demographics                | X   |   |
| Male sexual function        | X   | X   |
| Female sexual function      | X   | X   |
| QOL (FACT-BMT)              | X   | X   |
| Depression/Anxiety (HADS)   | X   | X   |
| Depression (PHQ-9)          | X   | X   |

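### The efficacy baseline precedes an untreated wait that nothing measures, so the 6-month change mixes natural course and regression to the mean with any intervention effect

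*Combined protocol and SAP*

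**What the plan says.** - **Entry.** The third eligibility criterion is "Positive screen for sexual dysfunction that is causing distress based on the NCCN survivorship guidelines". Section 4.1 applies it as a two-question screen given by the transplant clinician at a routine clinic visit.
- **Baseline.** "Study participants will complete baseline self-report assessments at the time of obtaining informed consent for the study", or within 72 hours of enrollment (4.1).
- **Wait.** Patients are then booked for their "first study intervention visit on the same day as their regularly scheduled subsequent follow-up visit" (4.1). No typical or maximum interval is given.
- **Rescreen.** The interventionist screens again at the start of that visit. "If patients no longer experience sexual dysfunction before their initial study visit, they will be considered ineligible for the study" (5.2). They still count towards accrual but do not receive the intervention. No expected rate is given.
- **Measurements.** "We will administer the following questionnaires at baseline and 6 months after enrollment" (5.3). Section 5.4 and Table 1 list the same two occasions, so no questionnaire is repeated at visit 1.
- **Analysis.** The hypothesis for objective 2 is "Participants will have improved sexual function, QOL, and mood at 6 months post-intervention compared to baseline" (section 2). Section 7.5 tests it by paired t-tests, with McNemar tests for the dichotomised mood outcomes. There is no comparator, and natural course and regression to the mean are not mentioned.
- **6-month anchor.** Section 5.3 and Table 1 count from enrollment; section 7.5 counts from the initial intervention visit. The baseline precedes the wait under either rule.

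**The concern.** A patient's symptom score varies around a personal level. People selected because they report a distressing problem on one day tend, as a group, to score worse that day than their own average, and to score better later whether or not they are treated. Here the only pre-treatment score is taken at that moment. An untreated interval follows, and the next score comes only after the intervention. Improvement during the wait, and drift back towards the usual level, both end up in the quantity that section 7.5 tests as preliminary efficacy.

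At stake is how objective 2 is read. A significant paired test would look like a signal for the intervention, and sections 1.1 and 1.2 say these data will help inform a large randomized study. The plan contains no measurement against which a reader could judge how much of the change would have occurred untreated, although visit 1 offers a ready point to take one.

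**Working it through.** **1. The plan's own figures.** The only precision statements concern feasibility. With n = 53:

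- 1.96 × √(0.75 × 0.25 / 53) = 0.117, stated as 12%
- 1.96 × √(0.80 × 0.20 / 53) = 0.108, stated as 11%

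Both reproduce. Neither bears on the efficacy change, for which the plan gives no SD, effect size, significance level or number of pairs.

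**2. Model (assumptions, not from the documents).** Scores are oriented so that higher is worse and have SD 1. Any two occasions correlate ρ (0.6 to 0.8). The screen rests on a latent value that correlates r (0.5 to 1.0) with the score that day, and half of patients screen positive. Screen error is independent between occasions. There is no intervention effect and no natural drift. Occasions are consent (1), visit 1 (2) and 6 months (3). Patients are retained only if positive at both 1 and 2, as in section 5.2.

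- Probability of being positive twice: P = 1/4 + arcsin(r²ρ) / (2π)
- Expected spurious improvement from consent to 6 months in retained patients: r(1 − ρ) × 0.3989 × 0.5 / P
- Chance of declaring improvement: upper tail of the noncentral t for a two-sided 5% paired test, noncentrality = (improvement / SD of change) × √n, n = 40 pairs

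The SD of change in retained patients was obtained by simulation and is slightly below √(2(1 − ρ)). The simulation also confirmed the closed form.

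| ρ | r | P | Spurious improvement (SD) | SD of change | Improvement declared, 40 pairs |
|---|---|---|---|---|---|
| 0.8 | 0.5 | 0.282 | 0.07 | 0.63 | 10% |
| 0.7 | 0.7 | 0.306 | 0.14 | 0.76 | 20% |
| 0.6 | 1.0 | 0.352 | 0.23 | 0.83 | 39% |

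Middle row: r²ρ = 0.343; P = 0.25 + 0.350 / 6.283 = 0.306; improvement = 0.7 × 0.3 × 0.1995 / 0.306 = 0.137; noncentrality = 0.137 / 0.757 × 6.325 = 1.14. The nominal rate in that direction is 2.5%. With 20 pairs, roughly a single-sex outcome, the range is 7% to 21%.

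**3. Sensitivity.**

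- If screen error is a stable trait of the patient, the two screens correlate r²ρ + 1 − r² = 0.853 at 0.7/0.7. Then P = 0.413, the improvement is 0.21 × 0.1995 / 0.413 = 0.10 SD, and the test declares improvement in about 13% of trials.
- Implied rescreen failure is 1 − P/0.5: 39% with independent error and 17% with stable error. The observed failure rate would therefore help to show which case is nearer.
- If the rescreen is ignored, the formula becomes r(1 − ρ) × 0.798, giving 0.08 to 0.32 SD and 12% to 60%. That is not this protocol.

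**4. What a visit-1 questionnaire would show (0.7/0.7).**

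- Consent to visit 1, everyone attending: 0.7 × 0.3 × 0.798 = 0.17 SD.
- Consent to visit 1, retained patients only: 0.00, because both scores were selected in the same way.
- Visit 1 to 6 months, retained patients: 0.14 SD, the same as from consent.

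A visit-1 baseline thus removes true change during the wait but not regression to the mean in the retained group. Regression becomes visible only if rescreen failures are kept in the comparison.

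**The case against.** The strongest reply is that this is a pilot. Feasibility is primary and carries the go criteria; efficacy is secondary and repeatedly labelled preliminary; a randomized study is to follow. Every uncontrolled pilot shares the limit. The background describes the dysfunction as lasting many years, and patients are screened by clinic schedule, not because of a flare. This stands in part and limits the weight of the point. It does not remove it: regression to the mean needs only fluctuation around a stable level, and this design adds an untreated wait after its only baseline.

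Several stronger readings are tempting and are not supported:

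- *That the protocol expects patients to recover untreated.* Section 5.2 is conditional and gives no rate. It provides for loss of dysfunction before visit 1, no more.
- *That untreated recoveries are meant to enter the efficacy test.* Section 5.4 does speak of all participants, and 7.5 names no analysis set. But 5.2 makes rescreen failures ineligible for the study, and 7.5 counts time from an initial intervention visit. The text already points to excluding them; a clarifying sentence is enough.
- *That the bias could reach 0.32 SD, with 60% false improvement.* Those figures leave out the rescreen.
- *That moving the baseline to visit 1 cures the problem.* It does not, because the rescreen is itself a selection.
- *That the later trial's planning effect will be inflated.* The documents say only that the data will help inform that trial, not that the observed change will be its effect size.

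It is also fair that one screen correlation need not fit every outcome. Selection is on sexual dysfunction, so the effect on FACT-BMT, HADS and PHQ-9 may be smaller.

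**Conclusion.** The point holds for objective 2. As designed, the paired change from baseline to 6 months cannot separate the intervention from change during the wait, later natural course, or regression to the mean, and nothing in the plan measures the untreated course. Under the stated assumptions, regression alone gives about 0.07 to 0.23 SD and declares improvement in about 10% to 39% of trials with 40 pairs, against 2.5%. If screen error is stable, the figures at 0.7/0.7 fall from 0.14 to 0.10 SD and from 20% to about 13%. True natural recovery would add to these; its size cannot be derived from the documents. The feasibility criteria are untouched. This is a worthwhile low-cost improvement to a secondary analysis, not a flaw that undermines the study.

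**What to change.** 1. **Sections 5.2, 5.4 and Table 1:** every participant attending visit 1 repeats the existing REDCap questionnaires before the rescreen is done or acted on.
2. **Section 7.5, untreated course:** report the change from consent to visit 1 in all of these participants, including rescreen failures, beside the change to 6 months. Also report the proportion failing the rescreen and the interval since consent.
3. **Section 7.5, baseline:** use the visit-1 score as the pre-treatment baseline, so that true change during the wait is not credited to the intervention. State that this leaves regression to the mean in retained patients, and that a flat consent-to-visit-1 change in retained patients alone must not be read as showing none. The whole-group change indicates scale; it is not a figure to subtract.
4. **Section 7.5, analysis set:** limit the paired tests to patients who started the intervention, and reconcile the 6-month anchor with 5.3, 5.4 and Table 1.
5. **Conclusion on objective 2:** word it as within-person change. Natural course after visit 1 would still need a concurrent control.

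Cost: one extra short form completion at a visit already scheduled, and a short amendment. Items 4 and 5, and the two added counts in item 2, are wording or simple tabulation. The stated improvement may become less favourable.
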